6.3. Sample Size and Power

We also assess sample size based on the long-term adherence outcome of this pilot RCT, an increase in hair levels of TFV with the real-time feedback/monitoring in the intervention arm compared to the SOC arm. For the hair level outcome, we consider the simplified situation of estimating difference in hair level changes between intervention and control arms using a single post-intervention level from each person. In this scenario, and assuming the person-to-person variability in TFV hair levels observed in a similar population (women in Africa not in SDC) in VOICE,³⁵ then the standard deviation for the difference between a baseline and follow-up (log) TFV hair level is 1.2. We estimate the power for detect a difference using a two-sample t-test formula using the standard deviation the formula for two-sample t-test with 50 enrollees per arm, then we can detect a difference of 0.68 (log TFV) between two arm with 80% power and a difference of 0.79 (log TFV) with 90% power on a 0.05 level. This translate to differences of 2.0 fold and 2.2 fold in TFV levels, respectively. Clinical differences could be appreciably smaller so it is not our objective to find statistical significance in hair outcome but, instead, to examine the feasibility of the intervention and to generate suggestive data on effects on long term adherence assessed by hair levels of TFV.

6.4. Statistical analyses

Acceptability

For the questions on the acceptability survey with graded answers, frequency distributions of the Likert scale data will be summarized. The results of the survey question regarding the advantages and disadvantages of real-time monitoring of adherence will be tabulated, including manually reviewing and assigning open-ended responses under the "other" option to appropriate prespecified options. Qualitative interviews from the participants will be recorded, transcribed, and translated into English by the study team. The transcripts will be reviewed separately by two investigators for completeness and initial theme generation. Coding and analysis will be performed with Dedoose, using an integrated inductive-deductive approach informed by grounded theory. 197,198 Our approach permits us to organize our codes around themes in the semi-structured interview guides, while also leaving room for new codes to emerge. We will then review the results of our coding for consistency of text segmentation and code application with continued

inter-coder agreement. Inconsistent results will be reviewed by the coders until consensus on grouped themes is reached.

Feasibility

The feasibility of this intervention will be assessed by the proportion of women retained in the study at 12 months, the mean number of missed visits, and the proportion of planned urine assessments completed and messages delivered in the intervention arm. Uncertainty around these observed proportions will be described using 95% confidence intervals. For the interview data from providers to assess feasibility, we will use similar qualitative methods to analyze the data as described under *Acceptability*.

Long-term adherence metric

Our analysis (of the adherence outcome) will be a (censored) mixed effects linear regression model, also known as a mixed tobit model, to estimate the effect of the intervention versus SOC on logarithmically transformed levels of TFV in hair. Since large relative differences between very low hair levels are less clinically important than similar relative differences between higher levels, we will censor undetectable levels at the lower detection limit, and we will also add the detection limit to all levels before log-transformation. These steps reduce the influence of minor differences between levels at or near the detection limit, while preserving the approximate interpretation of back-transformed regression coefficients as fold-effects. The predictor variable for intervention will equal zero for everyone at the baseline (0-month) visit (where hair levels reflect prerandomization baseline) and then will change for those in the intervention arm to equal 1 at all subsequent visits. A random intercept term will account for within-person correlation across the multiple visits; time point will be included as a categorical variable to account for systematic changes over time. We incude the pre-intervention TFV hair levels in the tobit model Correlations between self-reported adherence and pill counts over 30 days and hair levels will also be calculated.

Analyses will be by intention-to-treat. PrEP tenofovir drug levels in hair will be compared between arms using repeated measures mixed effects tobit model with baseline hair TFV included as a baseline covariate. The hypothesis of statistically significantly higher TFV levels will be tested at the month 12 time point. PrEP discontinuation, defined as missing a refill, will be analyzed as a time-to-event outcome using Cox proportional hazards regression with the pre-intervention TFV hair levels as a baseline factor in the model. If PrEP is discontinued by the treating clinician for safety reasons (but not adherence reasons), follow-up thereafter will be censored. Adjusted analyses will be performed to control for potential confounders based on our prior work assessing correlates of PrEP use: demographics (e.g., age, educational level), sexual behaviors (e.g., condom use, outside partnerships), medical status (e.g., depression), and beliefs (e.g., risk perception, PrEP efficacy). Stata package "st" and "metobit" will be used for analyses.

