1.3. Schema

be assessed.

92

Purpose:	To determine if providing real-time monitoring/feedback via a POC				
. a. pood.	tenofovir urine assay will be acceptable to women, feasible for providers,				
	and improve adherence over time using a long-term metric of adherence				
	among women on PrEP in Thika, Kenya.				
Decima	· · · · ·				
Design:	A pilot randomized controlled trial of women receiving PrEP will be				
	randomized (1:1) to standard of care adherence counseling (n=60) vs				
	real-time adherence feedback and enhanced adherence counseling				
	using information from the POC urine assay (n=60)				
Population:	HIV-uninfected women ≥18 years old receiving PrEP in Kenya				
Study Size:	a minimum of 100 and not exceeding 120 participants equally				
	randomized to each arm.				
POC Testing:	Urine tenofovir testing by lateral flow assay				
Outcome	The primary outcomes for this study will be acceptability to participants,				
Measurement:	feasibility for providers, and impact of the POC adherence test on				
	measures of tenofovir in hair samples 12 months after randomization.				
Study Duration:	24 months, including enrollment period, and 12 months of follow-up per				
	participant.				
Primary Objectives:	To test the acceptability to participants, feasibility for providers, and				
	impact on a longer-term metric of adherence among participants				
	(assessed via tenofovir levels in hair) of implementing POC urine				
	tenofovir testing and providing real-time feedback among women				
	receiving PrEP in Thika, Kenya.				
Study Site:	The Thika Clinic, which is located in an urban center about 40 kilometers				
	outside of Nairobi, has been a center of excellence for PrEP delivery in				
	Kenya and a longstanding clinical research partner with KEMRI and the				
	University of Washington.				
	Offiverally of vivaalington.				

94 2. CONSORT DIAGRAM

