6. STUDY OUTCOMES AND ANALYSES

6.1. Primary Outcomes

The three primary outcomes for this study will be 1) acceptability of POC urine tenofovir testing among women receiving PrEP in Kenya; 2) feasibility to provide feedback on the POC urine tenofovir assay to participants for healthcare providers, and 3) long-term metrics of adherence as assessed via hair concentrations of TFV and FTC assessed at the 12-month study visit after enrollment.

964965966

967968

969

970

971

972973

974

975

976

977

978

979

980

981

982

983

984

985

986

6.2. Data Collection for Primary Outcomes:

Acceptability for participants taking PrEP: We will conduct a mixed-methods assessment of the intervention arm participants' (all women on PrEP) experiences with real-time monitoring and feedback at the end of the study. A quantitative survey and a qualitative interview guide for indepth interviews of participants will draw from the Information-Motivation-Behavioral skills (IMB) model. 180-187 Quantitative data collection will occur via standardized interviewer-administered questionnaires. Items to be assessed include the following: 1) Feelings about receiving their PrEP adherence results in real time; 2) Likelihood of participating in other studies using a similar design; 3) Likelihood of wanting to receive results of urine testing outside of a study while they are on PrEP; 4) Concern about the privacy and security of the data regarding their urine results; 5) Grading of the potential impact of knowing their urine TFV results on subsequent medication adherence; 6) Advantages and disadvantages of being told about their adherence in real time; 7) Likelihood of taking PrEP just before later study visits because they knew the urine test was being conducted; 8) Preferences regarding a yes/no assay versus an assay that provides information on "high", "moderate" or "low" adherence. A 5-point Likert item format will be used to assess graded items (such as the likelihood of wanting continued urine testing in the context of PrEP; feelings about the urine testing, ranging from negative to positive; concerns about privacy, ranging from low to high; the potential impact of real-time feedback on subsequent adherence, ranging from low to high). Other items (advantages and disadvantages of being told about adherence results) will provide pre-specified options with one "other" option for open-ended text fields.

987 988

989

990

991

992

993

994

995

996

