Small hair samples (~50-100 strands) will be collected at study visits using previously described methods.²³ TFV concentrations in hair samples will serve as the metric for cumulative, long-term adherence to PrEP. TFV and FTC are measured in hair samples at the Hair Analytical Laboratory at the University of California San Francisco (UCSF) using validated methods. The Hair Analytical Laboratory (HAL), and its predecessor (the UCSF Drug Studies Unit), have vast expertise (since 1977) in LC-MS/MS-based methods to analyze drugs in a variety of matrices, including

antiretrovirals (ARVs) in hair. 9,10,30 The trial will assess whether TFV levels in hair increase over time with delivery of the feedback results and the opportunity to perform enhanced adherence counseling. Moreover, the combination of short-term adherence metrics (urine tenofovir assay) and long-term adherence metrics (hair TFV assay) in this study will enable us to determine if there are white-coat patterns of adherence. 35,39,41 For example, positive urine TFV assays but low concentrations of TFV in hair (in intervention arm participants or in both arms, as assessed at the end of the study) are suggestive of white-coat adherence patterns. PrEP refills will be measured through data from the clinic's electronic pharmacy system.

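### The hair model's single arm term estimates an average effect over months 3 to 12, but the outcome and its test are set at month 12 and no month-12 contrast is written

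*Combined protocol and SAP*

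**What the plan says.** Section 6.4 (long-term adherence metric) describes a mixed tobit model for log hair TFV with a random intercept. Its first paragraph defines the only arm term in the plan: "The predictor variable for intervention will equal zero for everyone at the baseline (0-month) visit", and it "then will change for those in the intervention arm to equal 1 at all subsequent visits". On visits it says that "time point will be included as a categorical variable to account for systematic changes over time". It names no product of arm and visit.

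The second paragraph again names a repeated-measures mixed tobit model, now "with baseline hair TFV included as a baseline covariate", and adds: "The hypothesis of statistically significantly higher TFV levels will be tested at the month 12 time point".

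Two other places fix the time point. Section 6.1 gives the third primary outcome as "hair concentrations of TFV and FTC assessed at the 12-month study visit after enrollment", and the schema in section 1.3 gives "measures of tenofovir in hair samples 12 months after randomization". The hair paragraph of section 6.2 is looser: "The trial will assess whether TFV levels in hair increase over time with delivery of the feedback results".

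**The concern.** A model with one 0/1 post-baseline arm term and visit as a main effect forces the arm difference to be the same at months 3, 6, 9 and 12. Its coefficient is a pooled effect and has no month-12 component to test. The stated outcome and the stated test are both at month 12. Two analysts following section 6.4 could therefore report different quantities as the primary hair result.

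The two quantities agree only if the effect is constant, or if the month-12 effect happens to equal the average. The plan states neither, and a constant effect is not obvious. Under section 5.5 feedback is given at month 0 and every quarter, so month-3 hair follows one feedback session and month-12 hair follows four. The effect could build, or it could fade as the novelty wears off.

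The stake is the size and label of the estimate. Section 6.3 says the hair result is meant to be suggestive, and section 3.5 says the pilot should inform a larger trial. A pooled coefficient labelled as month 12 understates a building effect and overstates a fading one.

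**Working it through.** **Inputs from the documents.** Section 6.3: 50 per arm, SD of change in log TFV 1.2, detectable differences 0.68 (80% power) and 0.79 (90% power) at the 0.05 level. Section 5.2: hair at months 0, 3, 6, 9 and 12.

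**Assumed.** Within-person correlation ρ = 0.5 (range 0.3 to 0.7); the effect trajectories; complete, uncensored data unless stated. The documents give none of these.

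**1. The plan's own figures.** The planning SE is 1.2 × √(2/50) = 0.24. A two-sided two-sample t-test gives power 80.1% for 0.68 and 90.3% for 0.79, and exp(0.68) = 1.97, exp(0.79) = 2.20. The stated figures reproduce.

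**2. What the single coefficient estimates.** Generalised least squares for the written model (random intercept, five categorical visits, one post-baseline arm term) puts weight 0.25 on each of the month 3, 6, 9 and 12 effects, at ρ = 0.3, 0.5 and 0.7 alike. Hence

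pooled − month 12 = −0.75 × (month-12 effect − mean effect at months 3, 6 and 9).

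Each 0.1 log units of gap moves the estimate by 0.075.

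**3. Illustrations.**
- Building 0.17/0.34/0.51/0.68: pooled = 1.70/4 = 0.425 (1.5-fold); the month-12 effect is 0.68 (2.0-fold). Check: 0.68 − 0.75 × (0.68 − 0.34) = 0.425.
- Fading 0.6/0.4/0.2/0: pooled = 1.2/4 = 0.30 (1.35-fold); the month-12 effect is 0. Check: 0 − 0.75 × (0 − 0.4) = 0.30.

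**4. Precision.** An SD of change of 1.2 gives residual variance 1.2²/2 = 0.72 and total variance s² = 0.72/(1 − ρ), which is 1.44 at ρ = 0.5. With baseline used once:
- Month-12 contrast: SE = √[s²(1 − ρ²) × 2/50] = √(1.08 × 0.04) = 0.208.
- Pooled term: SE = √[s²(ρ + (1 − ρ)/4 − ρ²) × 2/50] = √(0.54 × 0.04) = 0.147.

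| ρ | Pooled SE | Month-12 SE | Month-12 power for 0.68 |
|---|---|---|---|
| 0.3 | 0.126 | 0.193 | 94% |
| 0.5 | 0.147 | 0.208 | 90% |
| 0.7 | 0.165 | 0.221 | 87% |

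Keeping month 0 as an outcome row with the arm effect fixed at zero, or using it as a covariate with months 3 to 12 as outcomes, gives the same SEs.

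**5. Baseline used both ways.** Read together, the two paragraphs of section 6.4 keep month 0 as an outcome row and also enter baseline hair TFV as a covariate. In 4,000 simulated null trials (uncensored, random-intercept REML, ρ = 0.5):
- Month-12 contrast: reported SE 0.187 against an actual 0.214; null rejection 8.8% (7.6 to 9.4% for ρ = 0.3 to 0.7).
- Pooled term: reported SE 0.116 against an actual 0.153; null rejection 13.9% (11.9 to 15.2%).
- Either single use: rejection 4.7 to 5.9%, with reported and actual SEs in agreement.

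**The case against.** The best case for the plan is that the time point is already fixed. Sections 1.3, 6.1 and the second paragraph of 6.4 all say month 12, and the 0/1 coding stands only in the first paragraph of 6.4. An average-effect model followed by a separate month-12 test is a natural reading, and nothing says the pooled coefficient will be reported as month 12. That reading is possible, but the second paragraph supplies no term or contrast to carry it out, and the only arm coding given cannot do so. More than a detail is missing.

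Every non-zero discrepancy rests on an assumed trajectory, and under a constant effect the pooled term is unbiased and more precise. This is true. The −0.75 relation, however, holds for any trajectory with complete, uncensored data, and the plan never states that it assumes a constant effect.

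Uneven missed visits would shift the weights. With assumed rates of 10/15/20/30% the month-12 weight falls to 0.21. But sections 5.5 and 5.12 make final-visit hair a retention target, so the shift could go the other way. That point stands, and the conclusion does not rely on the 0.21.

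The double use of baseline is a separate defect, and if the two paragraphs describe two models it may not occur. It is included only because a month-12 contrast added to the text as it stands would inherit it. The simulated rates come from an uncensored fit, not the planned tobit.

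Finally, section 6.3 disclaims significance as an aim for hair. That limits the harm to the effect size and its label.

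**Conclusion.** The concern holds. The model as written yields one coefficient, the equal-weight average over months 3, 6, 9 and 12 with complete, uncensored data, while the outcome and its test are at month 12. The error from reporting one as the other is 0.75 times the gap between the month-12 effect and the mean of the three earlier effects. It is zero if the effect is constant and about 0.26 to 0.30 log units in the two assumed trajectories. Missed visits and censoring change the weights, but the coefficient stays a pooled post-baseline effect. With no effect at any visit, and baseline used in one way only, the 5% error rate is unaffected. The phrase about levels rising over time in section 6.2 does not settle which quantity is primary. This should be corrected before the hair data are analysed.

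**What to change.** In section 6.4:

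- Replace the single arm term with arm-by-visit terms at months 3, 6, 9 and 12, and name the month-12 contrast with its 95% CI as the primary hair analysis.
- Keep the pooled coefficient as a secondary summary, labelled as the average over months 3 to 12.
- Use baseline hair TFV once: either as a month-0 outcome row with the arm effect fixed at zero, or as a covariate with only months 3 to 12 as outcomes. Adding the contrast without this step is not enough.
- If the average is what is intended, say so in sections 1.3, 6.1 and 6.4 in place of month 12.

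The change costs SAP wording and three parameters. It also costs precision if the effect is constant, as tabulated above. The month-12 SE will not always stay below the planning value of 0.24. With an assumed 30% of post-baseline visits missed at random it is 0.242 (power for 0.68 80%; SE 0.228 to 0.255 and power 85 to 76% for ρ = 0.3 to 0.7). The planning t-test with 30% missing would itself have SE 0.24/√0.7 = 0.287. A simulated random-intercept tobit (300 trials, ρ = 0.5, an assumed 30% of values censored, without the step of adding the detection limit) gives SE about 0.23 and power 84% at 15% missed, and about 0.25 and 77% at 30% missed.

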participants had tenofovir diphosphate (TFV-DP, measured in dried blood spots) levels consistent with 4 doses a week (albeit women may need dosing 7 doses a week) at 3-months with only 9% of women with similar levels at 12 months. 142 Pharmacokinetic modeling indicates that, due to differences in TFV exposure in vaginal versus rectal tissues, 50 women likely require higher levels of adherence, specifically 6-7 doses PrEP/week. 143 These data highlight the importance of bringing novel adherence interventions to women on PrEP, which is why we chose to study women in our initial pilot study of this important new assay.

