Upon randomization, study visits will occur at 0 (baseline visit), 3, 6, 9 and 12 months after study enrollment. Each visit will include rapid testing for HIV, pregnancy testing if the participants requests it or is unsure of being pregnant (per standard of care), and creatinine measurement (per 2016 Kenya PrEP guidelines), as well as adherence counseling. As per the 2016 Kenya PrEP guidelines, any other laboratory testing or assessments will be performed per the history and physical examination. Self-reported time since last PrEP dose taken will be collected via a visual analog scale, as will self-reported adherence over the previous 3 and 30 days. The Urine samples will be collected at every visit for participants in both arms, but stored only for participants in the standard-of-care arm (to be tested locally, in batches by laboratory staff not involved in daily study conduct). Urine samples will only be tested via the tenofovir assay in real-time for participants in the intervention arm by laboratory staff at the Thika Clinic. The results of the urine assay for intervention arm participants will then be recorded by the laboratory staff and conveyed to the research providers of intervention arm participants who will proceed to immediately provide feedback to participants using counseling guides prepared prior to the trial (and informed by the

results of the formative work to qualitatively assess how to provide supportive counseling message for either yes adherence or no adherence, **Section 3.4**).

Hair samples will be collected at each study visit (months 0, 3, 6, 9 and 12) for storage and testing at the end of the study for all participants. (Please see **Section 3.1** for a discussion of how white-coat adherence patterns can be assessed by collecting both short-term and long-term adherence metrics). Feasibility and acceptability assessments will be conducted at study end for research providers (feasibility) and participants in the intervention arm (acceptability), respectively. Plasma and DBS for TFV and TFV-DP level measurement, respectively, will be collected at each visit in each arm as additional adherence metrics and stored for future analysis in the UCSF Hair Analytical Laboratory (HAL) after seeking independent funding for those concentrations.

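### Section 6.4 relies on a random intercept alone for within-woman correlation; if that correlation decays, the month-12 hair test can exceed its 5% level and the interval is too narrow

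*Combined protocol and SAP*

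**What the plan says.** Hair is collected at months 0, 3, 6, 9 and 12 (section 5.2). Section 6.4, under the long-term adherence metric, models log hair tenofovir by a mixed tobit regression:

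- Correlation: "A random intercept term will account for within-person correlation across the multiple visits".
- Time: "time point will be included as a categorical variable to account for systematic changes over time".
- Intervention: one indicator, zero for everyone at baseline, which "then will change for those in the intervention arm to equal 1 at all subsequent visits".
- Baseline: the arms are also compared by a "repeated measures mixed effects tobit model with baseline hair TFV included as a baseline covariate".
- Test: "The hypothesis of statistically significantly higher TFV levels will be tested at the month 12 time point".

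The Stata command metobit is named. The section mentions no robust or clustered variance, no serial or unstructured covariance, and no arm-by-visit term.

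**The concern.** A random intercept imposes the same correlation between months 0 and 12 as between months 9 and 12. If a woman's adherence drifts over the year, adjacent hair levels will agree more than distant ones. The model then misjudges how much the other visits tell us about month 12, and its standard error is too small. Hair level is one of three primary outcomes (section 6.1) and the only one with a between-arm test. The pilot is also meant to inform a larger trial, so the interval for the fold-effect matters even to a reader who ignores the p-value.

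The size depends on two matters the plan leaves open. One is how a month-12 test comes out of a model with a single intervention coefficient. The other is whether the baseline level is an outcome row, a covariate, or both.

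**Working it through.** **Inputs.** 50 per arm, SD of change in log level 1.2, 5% level (section 6.3); five visits (section 5.2); model terms (section 6.4). The visit correlation is not in the documents. I assume ρ between adjacent visits and ρ^j for visits j apart, with ρ from 0.5 to 0.9. Model-based errors are inferred from the plan's silence.

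**The plan's own figure.** SE = 1.2 × √(2/50) = 0.24. The two-sided t-test calculation gives detectable differences of 0.679 (80% power) and 0.786 (90%), against 0.68 and 0.79 stated; exp(0.68) = 1.97 and exp(0.79) = 2.20. These reproduce. They describe a t-test on one follow-up level, so they say nothing about the error rate of the mixed model, for which the plan gives no figure.

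**Hand calculation at ρ = 0.8** (unit variance; all variances in units of 2/n). The random-intercept fit settles near the average of the ten pairwise correlations: c = (4ρ + 3ρ² + 2ρ³ + ρ⁴)/10 = (3.2 + 1.92 + 1.024 + 0.4096)/10 = 0.655. The true month 0 to 12 correlation is ρ⁴ = 0.410.

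- (a) Month-12 contrast, baseline an outcome row with common mean. The estimate is d12 − c·d0. Model variance: 1 − c² = 0.5705. True variance: 1 + c² − 2cρ⁴ = 0.8926. SE ratio: √(0.5705/0.8926) = 0.80. Rejection: 2[1 − Φ(1.96 × 0.80)] = 11.7%.
- (b) Month-12 contrast, baseline as covariate only. The model pools the residual variances 1 − ρ^(2j) over four visits: (0.3600 + 0.5904 + 0.7379 + 0.8322)/4 = 0.6301. The true month-12 value is 0.8322. SE ratio 0.87; rejection 8.8%.
- (c) Single on/off term, baseline an outcome row. Model variance: c + (1 − c)/4 − c² = 0.3120. True variance: 0.7740 + c² − 2c(0.5904) = 0.4296, where 0.7740 = [4 + 2(3ρ + 2ρ² + ρ³)]/16 and 0.5904 is the mean of ρ^j over the four later visits. SE ratio 0.85; rejection 9.5%.
- (d) Single on/off term, baseline as covariate only. An average of four visits depends only on the average variance and covariance, which the random intercept reproduces, so the test stays near 5%.

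**Simulation under no effect** (random-intercept fit, model-based Wald test, complete uncensored data, 4,000 runs, Monte Carlo error about 0.3-0.6 points), rejection in %:

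| Specification | ρ 0.5 | 0.6 | 0.7 | 0.8 | 0.9 |
|---|---|---|---|---|---|
| (a) month 12, outcome row | 7.3 | 8.3 | 10.0 | 11.9 | 14.2 |
| (b) month 12, covariate only | 5.9 | 6.8 | 7.9 | 8.9 | 10.9 |
| (c) single term, outcome row | 8.6 | 8.4 | 8.9 | 10.0 | 10.8 |
| (d) single term, covariate only | 6.4 | 5.5 | 5.7 | 5.7 | 5.9 |

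**Variations.**

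- Constant correlation of 0.6: 4.9-5.7%, so decay is the cause.
- 25% dropout: (a) 7.5-14.3%, (b) 7.0-11.8%.
- Tobit with 30% censoring (800 runs; ρ 0.5, 0.7, 0.8, 0.9): (a) 6.1, 8.9, 12.5, 15.1%; (b) 5.9, 7.5, 8.4, 9.8%; (d) 5.4-6.0%.
- Decay from permanent discontinuation at an assumed 10-30% per quarter, baseline an outcome row: month-12 contrast 6.4-9.4% and single term 9.3-10.4% where the SD of change was 1.06-1.12, near the plan's 1.2. A larger assumed fall, with SD 1.4-1.5, gave 6.3-12.4% and 14.5-15.2%.

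**With errors clustered on the woman:** 5.1-6.0% in every specification (3,000 runs, complete uncensored data); 4.5-6.3% in the discontinuation scenarios.

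**The case against.** A reader might infer that the month-12 test simply runs at 10-15%, two to three times its nominal level. The documents do not support that. Those rates need a visit-specific contrast, baseline kept as an outcome row, and ρ of about 0.7 or more. Section 6.4 writes no such contrast and says baseline enters as a covariate; read as the single term with baseline as covariate only, the test is close to nominal. Pure serial correlation also leaves no room for visit-level noise. With 30% of the variance as independent noise (an assumption), case (a) falls to 7.3-8.1% and (b) to 6.9%. All of this stands, and it is why the result is a range.

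A reader might also infer decay from section 3.1, which reports 25% of women at 3 months and 9% at 12 months with levels matching four doses a week in another study. That is a fall in a population proportion, which categorical time absorbs. It says nothing about within-woman correlation by lag.

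Two further points carry weight. The plan does not rule out robust errors; it is silent. Section 6.3 also says statistical significance in the hair outcome is not the objective, and no stated decision hangs on the test. That lowers the severity but does not remove the point: section 6.4 still specifies a significance test, and suggestive data need honest intervals. Nor is the near-nominal reading clearly the plan's, since setting the indicator to zero at baseline has a role only if baseline rows are in the outcome, and a single term does not isolate month 12.

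**Conclusion.** The point holds conditionally. If correlation between quarterly hair levels decays, model-based errors from a random intercept alone are too small for a month-12 comparison. Allowing for Monte Carlo error and the dropout and censoring checks, the nominal 5% test rejects under no effect about:

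- 7-15% for a month-12 contrast with baseline as an outcome row;
- 6-12% for that contrast with baseline as covariate only;
- 8-12% for the single term with baseline as an outcome row;
- 5-7% for the single term with baseline as covariate only.

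At ρ = 0.8 the month-12 interval is about 20% too short in the first case and 13% in the second. The assumptions are the decaying correlation, the censoring share and the use of model-based errors; none is stated in the documents. Under constant correlation there is no problem. Severity is low to moderate.

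**What to change.** In section 6.4 add: *Standard errors for the intervention effect will be cluster-robust (sandwich) by participant.* In the same paragraph, state the arm-by-visit term from which the month-12 contrast is taken, and whether baseline hair level is an outcome row or a covariate. It should not be both: that combination rejected in 9.1% (month-12 contrast) and 15.3% (single term) of null trials even under constant correlation, which is a separate defect. A random slope or unstructured covariance could be shown as a check.

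The cost is one option in the model call and a few lines of text. Intervals become somewhat wider if correlation decays and are essentially unchanged if it does not. The correction to about 5-7% was checked on uncensored data, so a short simulation with the tobit model and the expected share of undetectable levels would be sensible before the analysis is fixed.
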